6.5. Safety Assessments

6.5.1. Adverse Events

All AEs, regardless of causality or seriousness, will be collected from the time the patient/parent(s)/legal guardian(s) provides written informed consent/assent through 30 days after final dose of study drug (Safety Follow-up TCs, Section 7.5). Adverse event recording at the Safety Follow-up TCs will include inquiries regarding signs and symptoms of arrhythmia, any other cardiac manifestations [e.g., syncope], and psychiatric events [e.g., suicidality, compulsive behavior, anxiety]). Additional safety information, including the definition of an AE/SAE and reporting requirements, is provided in Section 8.

Clinically significant findings for laboratory test results, vital signs, ECGs, and abnormal physical examination findings should be recorded as AEs; a clinical diagnosis, rather than the changes in laboratory analyte or other assessment should be recorded.

6.5.2. Physical Examinations

Full or abbreviated physical examinations will be performed at study visits as detailed in Section 7. Full physical examinations will include an evaluation of the head and neck as well as cardiovascular, respiratory, gastrointestinal, neurological, dermatological, and musculoskeletal systems. Abbreviated physical examinations will be performed based on patient/caregiver-reported symptoms.

Height and weight will be measured using standardized methods and recorded on a standardized growth chart per Centers for Disease Control and Prevention (CDC) recommendations (CDC Clinical Growth Charts). Height will be recorded at Screening and at the EOT/ET Visit during the Double-Blind Treatment Phase and at every on-site visit during the OLE Phase. Body weight will be recorded at every on-site study visit.

6.5.3. Vital Signs

Vital signs will include blood pressure, heart rate, respiratory rate, and body temperature and will be measured at on-site study visits as detailed in Section 7. Patients should be resting for at least 5 minutes before measuring vital signs.

Vital sign measurements will be performed before blood samples are collected for clinical laboratory testing.

6.5.4. 12-Lead Electrocardiograms

12-lead ECGs will be obtained in triplicate for all patients at every on-site study visit as detailed in Section 7. Patients should be resting for at least 5 minutes before the first ECG is performed. All pediatric 12-lead ECGs will be read by a pediatric cardiologist.

ECG testing is to be performed before blood samples are collected for clinical laboratory testing.

Electrocardiogram findings that require discontinuation from the study are specified in Section 4.4.1.

In the Double-Blind Treatment Phase, clinically significant ECG findings (other than those requiring discontinuation from treatment) will require evaluation by the Investigator in consultation with the Medical Monitor.

In the OLE Phase and as noted in Section 4.4.2, any ECG reading that demonstrates QT prolongation should be promptly addressed by the Investigator. For clinically significant ECG findings, a follow-up ECG should be performed within 24 hours and again 7 days later to ensure the abnormality is not worsening. Follow-up 12-lead ECGs may be performed locally, with the results sent to the Investigator. At the discretion of the Investigator and in consultation with the Medical Monitor, pitolisant dosing may be temporarily stopped (interrupted) for 2 to 3 days based on clinically significant ECG findings. During an interruption, 12-lead ECGs will be performed daily. Upon resolution of the ECG abnormality, pitolisant administration may resume at the same dose as before the interruption, or the pitolisant dose may be lowered by 50%. If the condition persists after the interruption in dosing, the Investigator, in consultation with the Medical Monitor, will decide whether treatment should be permanently discontinued.

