1.4. Potential Risks and Benefits

The overall safety/tolerability profile of pitolisant at doses of 4.45 to 35.6 mg once daily has been well characterized from 41 completed studies. Of the 41 completed studies, 19 were Phase 1 studies and 22 were Phase 2/3 studies in the indications of narcolepsy, obstructive sleep apnea, Parkinson's disease, epilepsy, schizophrenia, Lewy body dementia, and attention deficit hyperactivity disorder (i.e., 8 narcolepsy and 14 non narcolepsy studies). The Phase 2/3 data comprised a total of 1513 patients who were treated with pitolisant; 1043 of these patients received pitolisant in double-blind, placebo-controlled studies. The most frequently reported (≥5%) treatment-emergent AEs (TEAEs) in patients who received pitolisant in the Phase 2/3 studies were headache (13.5%), insomnia (8.5%), and nausea (5.8%); the majority of these events were considered treatment-related.

Pitolisant is extensively metabolized by the liver and there is a significant increase in pitolisant exposure in patients with moderate hepatic impairment. Pitolisant prolongs the QT interval. The use of pitolisant should be avoided in patients with known QT prolongation or in combination with other drugs known to prolong the QT interval. Pitolisant should also be avoided in patients with a history of cardiac arrhythmias, as well as other circumstances that may increase the risk of the occurrence of torsade de pointes or sudden death, including symptomatic bradycardia, hypokalemia or hypomagnesemia, and the presence of congenital prolongation of the QT interval. The risk of QT prolongation may be greater in patients with hepatic or renal impairment due to higher concentrations of pitolisant. Pitolisant is contraindicated in patients with severe hepatic impairment and is not recommended in patients with end-stage renal disease.

In the clinical development program for pitolisant, there was no evidence of withdrawal syndrome from pitolisant or rebound effect upon discontinuation of therapy, and long-term studies did not demonstrate evidence of the development of tolerance to pitolisant. There were no clinically relevant effects of pitolisant on vital signs, electrocardiographic parameters, or laboratory findings across the database of patients exposed to pitolisant.

Additional information is provided in the WAKIX (pitolisant) Investigator's Brochure (IB) and current prescribing information for WAKIX (pitolisant).

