7.3.2.3. Visit 4 (Day 50 ± 3 Days)

To accommodate PK sample collection at Visit 4, patients will not take their daily dose of study drug before arriving at the study site. Patients and their caregivers will bring study drug and study diary with them to the study visit (time of study drug administration on the day before Visit 4 should be recorded in the study diary).

Study drug administration will be at the study site; the timing of study drug administration will be based on the PK sampling schedule.

Blood Sample Collection for PK:

A blood sample for PK analyses will be collected before administration of study drug at the study site (the time of sample collection is to be recorded).

After the first blood sample for PK analyses is collected, patients will be administered study drug (the time of study drug administration is to be recorded).

Additional blood samples for PK analyses will be collected at the following times after study drug administration (the time of each blood sample collection is to be recorded):

- Between 45 and 75 minutes after dosing
- Between 1.5 and 2.5 hours after dosing
- Between 3.0 and 4.0 hours after dosing
- Between 5.0 and 6.0 hours after dosing

The following evaluations will also be performed at Visit 4:

- Urine pregnancy test (FCBP only)
- Abbreviated physical examination
- Body weight
- Vital signs
- 12-lead ECG (in triplicate)
- C-SSRS (Appendix M)
- ADAMS
- Clinical laboratory tests (serum chemistry, hematology, urinalysis)
- Review of AEs
- Review of concomitant medications
- ESS-CHAD (parent/caregiver version)
- CaGI-S (for EDS)
- CGI-S (for overall clinical status related to PWS)

- ABC-C
- MERS-R-PWS
- Cogstate Detection Test
- Cogstate Identification Test
- Cogstate One Back Test
- ZBI-22
- HO-CT
- FSZQ
- Review study drug compliance/accountability (Section 5.5 and Section 5.6)

Blood draw volumes at Visit 3 are not to exceed the maximal allowable of 3.0 mL/kg per day (Appendix A and Table 10).

Patients will be dispensed study drug at this visit.

7.3.2.4. Visit 5 (Day 77 ±3 Days); End of Treatment in the Double-Blind Treatment Phase

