12.6.6 Electrocardiograms

Triplicate 12-lead electrocardiogram (ECG) will be obtained after the patient has been resting for at least 5 minutes. For clinically significant ECG findings, a follow-up ECG should be performed within 24 hours and again 7 days later to ensure the abnormality is not worsening. Follow-up 12-lead ECGs may be performed locally, with the results sent to the Investigator.

Heart rate, PR interval, RR interval, QRS duration, QT interval, QTcB interval, QTcF interval as well as investigator's interpretation of the ECG will be collected in the eCRF. All ECG results along with the investigator's interpretation, including the average of triplicate measurements at each timepoint, will be presented in data listings.

QTcF values will be presented with the implementation of corrections (i.e., Fridericia's) as defined in International Council for Harmonisation (ICH) Guidelines E14. Frequency count and percentage will be tabulated by the following categories. This summary will also be provided for each of age groups (6 to <10 years; 10 to <20 years and 20 to ≤65 years) and sex for the Double-Blind Treatment Phase. The same summaries by age groups and/or sex may be repeated for the OLE Phase.

Absolute QT interval corrected for heart rate based on Fridericia's formula (QTcF) prolongation:

- QTcF interval >442 ms (6 to <10 years old)
- QTcF interval >439 ms (10 to <20 years old)
- QTcF interval >450 ms (male, 20 to ≤65 years)
- QTcF interval >470 ms (female, 20 to \leq 65 years)
- QTcF interval >500 ms (regardless of age and gender)

Change from Baseline in QTcF interval:

- QTcF interval increases from Baseline 30-60 ms
- QTcF interval increases from Baseline >60 ms

In addition, potential QT prolongations will be categorized as:

- PR interval >300 msec
- QRS duration >140 msec
- PR interval increase from Baseline >50%
- QRS duration increase from Baseline >40%
- HR increase >65% from Baseline
- HR decrease >40% from Baseline

The actual values and change from Baseline values at each time point will be summarized for the safety populations. The overall interpretation will also be summarized by timepoint as well as the worst post-baseline.

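### The Visit 4 ECG has no set time relative to dose or PK sampling, so a predose QTcF is permitted at the one double-blind visit with a timed on-site dose and serial PK

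*Protocol*

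**What the plan says.** **ECG rules.** Protocol 6.5.4 says "12-lead ECGs will be obtained in triplicate for all patients at every on-site study visit as detailed in Section 7". It attaches two conditions: at least 5 minutes' rest, and "ECG testing is to be performed before blood samples are collected for clinical laboratory testing". Neither refers to the dose or to PK samples.

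**Visit 4 (Protocol 7.3.2.3).** "To accommodate PK sample collection at Visit 4, patients will not take their daily dose of study drug before arriving at the study site". A PK sample is taken first. On dosing the section says: "Study drug administration will be at the study site; the timing of study drug administration will be based on the PK sampling schedule". Four more PK samples follow at 45–75 min, 1.5–2.5 h, 3–4 h and 5–6 h. The triplicate ECG and the clinical laboratory tests appear in a list introduced by "The following evaluations will also be performed at Visit 4", with no times.

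**Visits 3 and 5.** The dose is taken at home on waking and its time is recorded (Protocol 5.4.1; double-blind Schedule of Assessments, footnote v). One PK sample is taken at any time after it and may share the laboratory draw.

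**QT risk.** Protocol 1.4 states "Pitolisant prolongs the QT interval" and links greater risk in hepatic or renal impairment to higher concentrations.

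**Analysis.** SAP 12.6.6 counts QTcF above age- and sex-specific limits, QTcF above 500 ms, and "QTcF interval increases from Baseline >60 ms". It summarises actual values and changes by time point. It uses neither time since dose nor concentration, and its list of ECG items collected in the eCRF names no ECG time. The exposure-response plots in SAP 12.4.1.6.6 concern efficacy measures.

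**The concern.** If the drug's QT effect depends on concentration, a QTcF reading is hard to interpret without knowing when it was taken relative to the dose. Visit 4 is the only double-blind visit where the dose is given on site at a known time with serial PK around it, so it is the natural place to measure QTcF against a known exposure. As written, the Visit 4 ECG may be taken about 24 h after the previous dose at one site and several hours after the new dose at another. Visit 4 values would then mix different exposures, and a difference from Visits 3 or 5 could reflect the clock rather than the drug.

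The stake is more than tabular. The same readings feed the QTcF thresholds in Protocol 4.4.1. Protocol 1.3.2 also supports the Amendment 6 regimens partly by QT risk estimated from population PK simulations, which observed QTcF-concentration pairs in PWS patients could have helped to check.

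**Working it through.** The plan states no figure on this point, so there is nothing to reproduce. The check sets the ECG order rule against the Visit 4 draw schedule.

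**Step 1. What the order rule allows.** Inputs: ECG before the clinical laboratory draw (Protocol 6.5.4); five PK draws, one predose and four post-dose (Protocol 7.3.2.3; Table 10 footnote). No section says when the Visit 4 laboratory tubes are drawn. Taking each PK draw in turn as the one they accompany:

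| Laboratory tubes drawn with | ECG allowed |
|---|---|
| Predose sample | Predose only |
| 45–75 min sample | Arrival to about 1.25 h post-dose |
| 1.5–2.5 h sample | Arrival to about 2.5 h post-dose |
| 3–4 h sample | Arrival to about 4 h post-dose |
| 5–6 h sample | Arrival to about 6 h post-dose |

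A predose ECG is permitted in all five cases and required in one. This is a list of possibilities, not a probability: the documents do not say which pairing sites use.

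**Step 2. Other visits.** There are three scheduled on-treatment double-blind ECG visits (3, 4 and 5). At Visits 3 and 5 the dose has normally been taken that morning, so those ECGs are post-dose at an unspecified interval. At most one of the three is predose by design.

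**Step 3. Remote Visit 4.** Under Protocol 6.6.1.2 the ECG may be done at home while the PK profile moves to the next on-site visit, an unscheduled visit or Visit 5. The ECG and the profile can then fall on different days.

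**Step 4. Illustrative size.** The documents give no half-life and no value for time to peak. Assume a single-exponential decline after the peak and a 24 h dosing interval:

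trough/peak = 2^(−(24 − tmax)/t½)

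- tmax 3 h: t½ 8 h gives 2^(−21/8) = 0.16; 10 h gives 2^(−21/10) = 0.23; 20 h gives 2^(−21/20) = 0.48.
- Lower end of a wider range: tmax 1 h, t½ 6 h gives 2^(−23/6) = 0.07.
- Upper end: tmax 5 h, t½ 36 h gives 2^(−19/36) = 0.69.

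If QTc change is also roughly proportional to concentration (a further assumption), a predose reading would show about 7% to 69% of the peak effect. This describes one predose reading, not the bias in the trial's outlier counts.

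**The case against.** The strongest case is that the gap is narrower than it looks.

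- **Trough is not established.** A reader might infer that Visit 4 QTcF will be measured at trough. The order rule concerns the clinical laboratory draw, not the PK draws or the dose. Permission to combine laboratory and PK draws is written for Visits 3 and 5, not Visit 4, and the patient is on site until 5–6 h post-dose. The Laboratory Manual, which is not among the documents, may settle the order. This stands: trough is permitted, and forced only if the tubes are drawn predose.
- **Most double-blind ECGs are post-dose.** A reader might infer that the outlier counts rest on trough readings, or that no ECG has an accompanying concentration. Visits 3 and 5 each have an ECG and a PK sample at the same visit with the dose time recorded, so neither inference holds. What is missing is a set ECG-to-sample interval and any analysis that uses it.
- **The SAP does not simply pool the readings.** It summarises values and changes by time point, and SAP Table 5 gives Visits 3, 4 and 5 separate windows. This also stands.
- **No objective calls for concentration-QTc work.** This is a proof-of-concept study, and Protocol 1.4 reports no clinically relevant electrocardiographic effects across the exposed database. That limits priority. It does not explain leaving timing open at the one visit equipped to control it.
- **It may be too late.** Protocol 1.3.2 describes the double-blind phase as completed. If so, Visit 4 wording cannot change these data.

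**Conclusion.** The point holds in a limited form. Neither the protocol nor the SAP fixes the Visit 4 ECG relative to dose or PK sampling. A predose ECG is always permitted and is required if laboratory tubes are drawn predose, so timing may vary between sites and patients. Visit 4 QTcF may therefore understate the on-drug effect, and the visit with the timed on-site dose and serial PK is not used for QT.

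The documents do not show that it will understate the effect, and they do not support a bias figure for the outlier counts. The 7% to 69% range rests wholly on assumed pharmacokinetics and an assumed proportional QTc response. It shows only that the consequence of a predose reading could be moderate or large. This is an inexpensive design improvement rather than an error that undermines the safety analysis.

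**What to change.** **Protocol, Visit 4 on site.** Take the existing triplicate ECG, after the 5-minute rest, immediately before one named post-dose PK sample, the same one for every patient. Draw the clinical laboratory tubes with or after that sample. The order rule in 6.5.4 is then met without an exemption.

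**Protocol, Visit 4 remote.** At the visit to which the PK profile is moved, time an ECG already due there in the same way.

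**Data collection.** Record the ECG clock time at Visits 3, 4 and 5. Dose times are already recorded.

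**SAP 12.6.6.** Add a descriptive plot of change in QTcF against the paired concentration.

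**Cost.** Protocol wording, one recorded time per visit, and one plot; no added ECG, blood draw or visit. The drawback is that the ECG may follow earlier PK venipunctures, which the rest period partly addresses.

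**If the double-blind phase is complete.** Only two parts can still be applied to these data: the plot, using any ECG times captured and labelled as an added analysis, and a stated limitation in the study report that ECG timing relative to dose was not controlled.

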6.5.5. Clinical Laboratory Tests

Clinical laboratory tests will include serum chemistry, hematology, urinalysis, pregnancy tests (serum and/or urine), and urine drug screens as detailed in Table 11. Samples for clinical laboratory tests (serum chemistry and hematology) will be collected as outlined in Section 7.

Consistent with the NIH Pediatric Blood Volume for Research Guidelines (Howie 2011), the total volume of blood collected is not to exceed the maximal allowable amount of 3.0 mL/kg per day (Appendix A). The approximate amount of blood to be collected for clinical laboratory tests at each visit is 9.0 mL (5.0 mL for serum chemistry tests and 4.0 mL for hematology tests).

The Laboratory Manual provides detailed instructions on sample collection, processing, and shipping procedures.

Laboratory test results will be reviewed by the Investigator. Any laboratory value outside of the normal reference range will be evaluated for clinical significance and, if deemed clinically significant, should be reported as an AE with an appropriate diagnosis.

Table 11: Clinical Laboratory Tests

| Urine Drug Screen -Amphetamines/stimulantsa -Barbiturates -Benzodiazepines -Cocaine metabolites -Opiates -Tetrahydrocannabinol -Phencyclidine Urinalysis -Specific gravity -pH -Blood -Glucose -Protein -Leukocyte esterase -Ketones -Bilirubin -Nitrites -Casts -Crystals -Erythrocytes -Renal tubular epithelial cells -WBCs -Bacteria Serum Drug Screen -Cannabidiola | Serum Chemistry (5.0 mL blood sample) -Albumin -Alkaline phosphatase -Alanine aminotransferase -Aspartate aminotransferase -Blood urea nitrogen -Calcium -Chloride -Creatinine -Creatine kinase -Glucose -High-density lipoprotein -Low-density lipoprotein -Phosphorus -Potassium -Sodium -Total bilirubin -Direct bilirubin -Total cholesterol -Total protein -Triglycerides -Uric acid -Ghrelin ^{a,b} Hematology (4.0 mL blood sample) -Complete blood count, including platelet count and WBC count with differential -Hemoglobin |
|---|--|
| Serum Drug Screen | |

FCBP = female of child-bearing potential; HbA1c = hemoglobin A1c; WBC = white blood cell

Note: Parameters will be assessed at study visits as detailed in the Schedule of Assessments for the Double-Blind Treatment Phase and the Schedule of Assessments for the OLE Phase.

6.5.6. Additional Safety Assessments

Suicide Risk/Suicidality

Suicide risk at Screening will be assessed through the use of the Very Young Child/Cognitively Impaired–Lifetime Recent C-SSRS (Appendix L). After Screening, suicidality will be evaluated at study visits and TCs through use of the Very Young Child/Cognitively Impaired-Since Last Contact C-SSRS (Appendix M). Any patient with active suicidal behavior or suicidal ideation will be excluded/withdrawn from the study (Section 4.1.2 and Section 4.4.1).

^a Required to be tested in the Double-Blind Treatment Phase only.

^b Acylated and unacylated ghrelin; patient must be fasting. Blood sample for ghrelin measurement may be taken at the same time as clinical laboratory test sample.

Seizure Disorder

In patients with a history of seizure disorders, the worsening of seizures or new onset seizures will be reported as AEs and the type, duration, and frequency of occurrence will be recorded in the eCRF. Patients who experience worsening of their seizure disorder should be withdrawn from the study.

Anxiety

The worsening of anxiety or new onset anxiety will be recorded as an AE. In addition, the ADAMS, a 28-item informant-rated scale designed to assess mood and anxiety symptoms will be administered (Esbensen et al 2003). The ADAMS questionnaire is provided in Appendix N.

6.6. Potential Use of Alternative Methods for Completing Study Assessments

To allow for greater flexibility and potentially decrease patient burden related to travel to the study site, specific study assessments may be completed by alternative methods (Table 12 and Table 13).

6.6.1. Assessments that may be Completed Remotely

Specific safety assessments including the assessment of AEs, administration of the C-SSRS and ADAMS, and the review of concomitant medications may be completed by the Investigator and/or site staff remotely using telemedicine technology.

Specific efficacy assessments including administration of the ESS-CHAD (parent/caregiver version), CaGI-S (EDS), CGI-S (overall clinical status related to PWS), ABC-C, MERS-R-PWS, ZBI-22, HQ-CT, and FSZQ may be completed by the Investigator and/or site staff remotely using telemedicine technology.

Other procedures including completing the informed consent process and study drug compliance/accountability review may be completed by the Investigator and/or site staff remotely using telemedicine technology. For patients utilizing the remote visit option, an on-site visit is required once a year. Remote visits cannot be consecutive.

